4 SAMPLE SIZE

Analysis of the Phase IIa study Efficacy and Tolerability of IRL790 in 74 PD patients with levodopa-induced dyskinesia (LID) on stable antiparkinsonian medication (NCT03368170) suggested that daily ON-time with troublesome dyskinesia decreased to an observed difference of approximately 1.6 hours (p=0.0274) among treated patients (n=39) versus placebo (n=36). Doseresponse analysis suggested a dose dependent effect with an observed difference vs. placebo around 4.6 h at the 7.5 mg dose. A pooled standard deviation of 3.2-3.3 hours was observed among the doses studied. This observed data provided the assumptions for the sample size calculation.

140 randomized patients (35 per group) are thought to be enough to demonstrate a treatment difference of 3 hours with pooled standard deviation 3.5, between a single dose level of active treatment and control (i.e., 2.5 mg, 5 mg, or 7.5 mg mesdopetam vs placebo b.i.d.) for the primary endpoint with 92% power using a hierarchical testing strategy, with key secondary endpoints tested using a truncated Hochberg procedure with truncation parameter γ equal to 0.7 for the 7.5 and then the 5 mg doses and a standard Hochberg procedure for the 2.5 mg dose to maintain control of the family wise error rate (FWER) at the nominal 0.05 level.

QMD Ref: Worldwide-TMP-ST-005-7.0 Effective: 12Aug2019	Governing QMD: Worldwide-SOP-ST-001	
Confidentiality Statement		
This document is the property of Worldwide Clinical Trials Inc. and may not be duplicated, copied, altered or removed from company without prior approval from Worldwide Quality Assurance or in compliance with Worldwide Standard Operating Procedures.		
REF: Worldwide-TMP-QA-001f-1.3	Page 11 of 49	

Worldwide Clinical Trials Controlled Quality Management Document		
WORLDWIDE CLINICAL TRIALS	Sponsor:	Integrative Research Laboratories Sweden AB
	Protocol Number:	IRL790C005
STATISTICAL ANALYSIS PLAN. PHASE 2-3-4		

The sample size calculation was based on an expected dropout rate of 10%, i.e., assuming 31 patients per group will provide evaluable data on the primary endpoint at Week 12. The actual dropout rate was evaluated by the Sponsor after 70 randomized patients had completed Visit 3 (Week 4) and due to a higher-than-expected dropout rate, it was decided to increase the sample size to 154 (+10%) randomized patients as permitted by the protocol.

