5 RANDOMIZATION

At the baseline visit (Visit 1, Day 1) patients will be randomized 1:1:1:1 to receive one of three doses of mesdopetam (2.5 mg, 5 mg, or 7.5 mg) or placebo b.i.d. based on the randomization schedule prepared by the unblinded statistician.

During the first week (Day 1 evening dose to Day 9 morning dose) a run-in phase with either 5 mg mesdopetam or placebo b.i.d. will take place, during which all patients allocated to mesdopetam will receive 5 mg mesdopetam b.i.d. and patients allocated to placebo will receive placebo b.i.d. The purpose of the run-in period with 5 mg b.i.d. is to allow for a one-week dose titration for patients randomized to 7.5 mg b.i.d. In a previous Phase 2a study most patients tolerated 5 mg b.i.d. At Visit 2 (Day 9), patients will receive mesdopetam 2.5 mg, 5 mg or 7.5 mg or placebo b.i.d., as randomized.

Randomization will be performed via a web-based Interactive Response System (IRS), using a dynamic balancing (minimization) algorithm. Randomization will be stratified by average (based on at least two valid home diaries) of <6 daily hours and \geq 6 hours of daily ON-time with troublesome dyskinesia at baseline.

During the one-week run-in phase, the IRS will ensure all patients allocated to mesdopetam treatment will receive 5 mg mesdopetam b.i.d., followed by the randomized dose during the treatment period. Patients allocated to placebo will receive placebo during the first week run-in and then continue placebo during the whole treatment period. Any dose reduction will also be managed through the IRS to ensure that blinding is maintained.

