6.1 Analysis Sets

6.1.1 Safety Analysis Set

The Safety Analysis Set (SAS) will include all randomized patients who received at least 1 dose of IMP. All safety and tolerability evaluations will be presented by the treatment received for the SAS.

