6.3.4 Summary Statistics

Continuous variables will be summarized by the number of non-missing observations, mean, median, standard deviation, and minimum and maximum.

Plasma concentration data will be summarized by number of non-missing observations (n), number of observations with concentrations below the limit of quantification (BLQ), arithmetic mean (mean), geometric mean, standard deviation (SD), median, minimum (min), maximum (max), and coefficient of variation (CV%). Concentrations that are BLQ will be set to zero for summary statistics. BLQ concentrations will be retained as BLQ in listings.

Categorical variables will be summarized by presenting the frequency and percent. Percentages will be based on the number of non-missing observations or the patient population unless otherwise specified. For each variable, all categories will be shown, including a category for missing where appropriate. Zero frequencies (but not the percent) within a category will be presented.

Incidences of adverse events, medical history and concomitant medications will be reported at the patient level. Patients can only be counted once within each PT and SOC under the highest severity and most related. Percentages will be calculated using the number of patients in the treatment group for the SAS. AE and medical history event tabulations will be presented by SOC and PT in

QMD Ref: Worldwide-TMP-ST-005-7.0 Effective: 12Aug2019	Governing QMD: Worldwide-SOP-ST-001	
Confidentiality	y Statement	
This document is the property of Worldwide Clinical Trials Inc. and may not be duplicated, copied, altered or removed from company without prior approval from Worldwide Quality Assurance or in compliance with Worldwide Standard Operating Procedures.		
REF: Worldwide-TMP-QA-001f-1.3	Page 21 of 49	

Worldwide Clinical Trials Controlled Quality Management Document		
WORLDWIDE CLINICAL TRIALS	Sponsor:	Integrative Research Laboratories Sweden AB
	Protocol Number:	IRL790C005
STATISTICAL ANALYSIS PLAN. PHASE 2-3-4		

descending overall frequency of incidence and then alphabetically for ties. Medications will be tabulated by ATC level 4 and preferred name in alphabetical order.

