- TEAEs Leading to Withdrawal of Study Drug
- TEAEs Leading to Early Termination from Study
- Deaths

TEAE tabulations will be presented by SOC and PT in descending frequency of AE incidence in the pooled mesdopetam arm and then alphabetically for ties.

All reported AEs will be listed in Appendix 16.2.7 of the CSR with separate listings for TEAE and non-treatment-emergent AEs (NTEAE).

Overall ongoing TEAEs will be summarized by month 1, 2, and 3. Additionally, TEAEs that occur in >5% of all participants will be summarized by month 1, 2, and 3.

QMD Ref: Worldwide-TMP-ST-005-7.0 Effective: 12Aug2019	Governing QMD: Worldwide-SOP-ST-001		
Confidentiality Statement			
This document is the property of Worldwide Clinical Trials Inc. and may not be duplicated, copied, altered or removed from company without prior approval from Worldwide Quality Assurance or in compliance with Worldwide Standard Operating Procedures.			
REF [·] Worldwide-TMP-OA-001f-1 3	Page $43 \text{ of } 49$		

Worldwide Clinical Trials Controlled Quality Management Document		
WORLDWIDE CLINICAL TRIALS	Sponsor:	Integrative Research Laboratories Sweden AB
	Protocol Number:	IRL790C005
STATISTICAL ANALYSIS PLAN. PHASE 2-3-4		

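### The monthly adverse-event tables use a frequency cut pooled over four arms and state no denominator of their own; a per-arm cut and an under-observation denominator would show the time course better

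*SAP*

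**What the plan says.** SAP 6.17.1 (Adverse Events) plans two displays over time. The first is "Overall ongoing TEAEs will be summarized by month 1, 2, and 3". The second, by event, reads: "Additionally, TEAEs that occur in >5% of all participants will be summarized by month 1, 2, and 3". Neither sentence names a denominator, and neither defines what makes an event ongoing in a given month.

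The general rule for adverse-event percentages is in SAP 6.3.4 (Summary Statistics): "Percentages will be calculated using the number of patients in the treatment group for the SAS". SAP 6.1.1 defines that set: "The Safety Analysis Set (SAS) will include all randomized patients who received at least 1 dose of IMP". No exception is made for later months.

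Three other parts of the plan bear on this:

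- **Allocation.** SAP 5 states that "patients will be randomized 1:1:1:1 to receive one of three doses of mesdopetam" or placebo.
- **Dropout.** SAP 4 records that "due to a higher-than-expected dropout rate, it was decided to increase the sample size to 154 (+10%) randomized patients". It gives no observed rate, overall or by arm.
- **Observation time.** Under Protocol 12.8, adverse events are collected up to the last follow-up assessment. For a patient who stops study drug early, Protocol 10.13 and 10.14 place that visit, if it can be done, 5 to 8 days after the last dose.

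**The concern.** The monthly tables exist to show whether events fade or persist. That question matters here: Protocol 4.6 reports that in the Phase 2a study nine mesdopetam patients had parkinsonism during titration only and two at steady state. Two features of the plan work against a clear answer.

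- **The cut.** A threshold set on all participants dilutes an event concentrated in one of four equal arms about fourfold. Its time course can be dropped even when it is common in that arm.
- **The denominator.** If the general rule carries over, patients who have left, and whose new events are no longer collected, still count in months 2 and 3. Percentages for newly observed events then tend to decline through attrition alone and can look like resolution.

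Only the time-course display is at stake. The overall adverse-event tables by arm are not affected by the cut.

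**Working it through.** **Inputs.** 154 randomized patients (SAP 4); equal allocation to four arms (SAP 5); a strict cut of more than 5% of all participants (SAP 6.17.1); a denominator of all dosed patients in the arm (SAP 6.3.4 with 6.1.1). I assume that all 154 are dosed. The prevalences and losses in steps 3 and 4 are also assumptions, because the documents give none.

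**1. The plan's own figure.** 140 × 1.10 = 154, as stated. 154 / 4 = 38.5, so arms of 38 or 39.

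**2. The pooled cut.** 0.05 × 154 = 7.7.

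- 7 patients: 7/154 = 4.5%, not in the table.
- 8 patients: 8/154 = 5.2%, in the table.
- All 7 in one arm: 7/38 = 18.4% or 7/39 = 17.9%, still not in the table.
- A less extreme split, with 4 in one arm and 1 in each of the other three: also 7 in total and left out, at 4/38 = 10.5% against 1/38 = 2.6%.

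With a cut of more than 5% in any arm, 0.05 × 38 = 1.9 and 0.05 × 39 = 1.95. Two patients in an arm are then enough (2/38 = 5.3%, 2/39 = 5.1%), and at most one patient per arm (about 2.6%) can be missed.

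**3. The denominator, within one arm.** Printed percentage = prevalence among those observed × (number observed / number dosed). Take an arm of 38, a 20% prevalence in month 3 among those still observed, and no contribution from leavers:

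| Lost before month 3 | Still observed | Printed |
|---|---|---|
| 0 | 38 | 20.0% |
| 4 | 34 | 20% × 34/38 = 17.9% |
| 8 | 30 | 20% × 30/38 = 15.8% |
| 12 | 26 | 20% × 26/38 = 13.7% |

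With the number observed as denominator, every row prints 20%.

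**4. The denominator, between arms.** Take a prevalence among those observed of 25% on an active dose and 20% on placebo:

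| Assumed attrition, active / placebo | Printed, active / placebo | Difference (5.0 points among those observed) |
|---|---|---|
| 10% / 10% | 22.5% / 18.0% | 4.5 points |
| 15% / 10% | 21.3% / 18.0% | 3.3 points |
| 25% / 8% | 18.8% / 18.4% | 0.4 points |

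Equal dropout scales both arms by the same factor and leaves their ratio unchanged. Only unequal dropout distorts one arm relative to the other.

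**The case against.** The case on the other side is substantial, and most of it stands.

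- **The denominator is inferred.** SAP 6.17.1 says only that events will be summarized; it neither names a denominator nor says that percentages will be printed. That stands. But SAP 6.3.4 is the one written rule, and a programmer who follows it would divide by everyone dosed.
- **The direction is not certain.** A reader might infer that arms losing patients will look safer. The documents do not establish this. They report no dropout by arm. Also, Protocol 12.8 follows adverse events only to resolution or the follow-up assessment, and SAP 6.2.5 imputes a completely missing stop date only for resolved events. A leaver's unresolved event could therefore be carried as ongoing into months 2 and 3 and push the percentage up.
- **An under-observation denominator has its own bias.** It removes patients who left because of adverse events and describes those who stayed. That stands, and the fix has to allow for it.
- **The 18% is the worst case.** It needs all seven cases in one arm and none elsewhere; one further case anywhere brings the event in. Every active arm takes the same dose during the run-in, which makes complete confinement to one arm less likely.
- **Little is hidden.** A reader might infer that dose-specific events vanish from the report. They do not. SAP 6.17.1 tabulates all TEAEs by system organ class and preferred term by arm without a cut, and lists every event. SAP 6.4 gives attendance at each visit, so approximate numbers still followed can be recovered.
- **The tables are supplementary.** Protocol 14.10.2 does not call for monthly tables, and Protocol 14.10 plans no formal safety testing.

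**Conclusion.** The point holds as a modest improvement to supplementary descriptive tables. The pooled cut is written in the SAP, and its effect is arithmetic: an event in up to 7 of 38 or 39 patients in one arm (about 18% at worst) can lose its monthly display, given 154 dosed patients. The denominator problem is conditional. If the SAP 6.3.4 rule is applied to months 2 and 3, and leavers contribute no events, a 20% prevalence prints as 13.7% to 17.9% after 12 to 4 losses from an arm of 38. Some downward drift needs only dropout, which SAP 4 says was above plan. Distortion between arms needs dropout that differs by arm, for which the documents give no figures. The documents do not support a claim that the safety conclusions are biased or that any event goes unreported.

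**What to change.** Amend SAP 6.17.1 in four respects:

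1. Define each month's denominator as the patients in that arm still under adverse-event observation at the start of the month, and print that number in the column for the month.
2. Count an event as ongoing in a month only for patients still under observation in that month.
3. State that the monthly tables are to be read beside the by-arm summary of TEAEs leading to withdrawal, since the new denominator drops patients who left because of adverse events.
4. Replace the pooled cut with more than 5% of patients in any treatment arm.

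The cost is a few sentences in the SAP and a change to one table program; no new data are needed. The drawback is longer tables, because two patients in one arm will be enough for an event to enter.

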6.17.2 Laboratory Data

Blood samples for analysis of serum chemistry, haematology and coagulation parameters will be collected at screening, Visit 1 (if 29 days or more between Screening and Visit 1), Visit 4, 5 and 6 and sent to the certified central laboratory for analysis. Urine analysis will be performed at the clinic using dip sticks. Descriptive statistics for observed values and change from baseline will be presented by treatment group and visit for each continuous haematology, serum chemistry (including thyroid panel), and coagulation parameter. A shift table for the change from baseline in dipstick urinalysis (Normal, Abnormal NCS, Abnormal CS) will also be provided.

Each continuous measurement will be classified as below, within, or above normal range, based on ranges supplied by the laboratory used. Shift tables in relation to the normal range from baseline to each follow-up visit will be presented.

Summaries and listings will be presented using the Système International (SI) unit for each parameter as received from the analytical laboratory.

A listing of any clinically significant laboratory measurements recorded throughout the study will be presented. All collected laboratory data will be listed. Any unscheduled samples analysed at local hospital laboratories will be listed separately with references ranges as provided by the analytical laboratory.

6.17.3 Vital Signs

Descriptive statistics for observed values and changes from baseline in the following vital signs will be presented by treatment group and visit:

- Systolic blood pressure (mmHg)
- Diastolic blood pressure (mmHg)
- Pulse rate (bpm)
- Body weight (kg)

Both standing and supine values, as well as orthostatic changes (standing – supine) will be presented for blood pressure and pulse rate. Measurements taken either seated or prone will be considered taken supine. The number and percentage of patients with either >20 mmHg reduction in systolic blood pressure after standing, or >10 mmHg reduction in diastolic blood pressure after standing, or both will be summarized. All vital sign data will be listed.

QMD Ref: Worldwide-TMP-ST-005-7.0 Effective: 12Aug2019	Governing QMD: Worldwide-SOP-ST-001	
Confidentiality Statement		
This document is the property of Worldwide Clinical Trials Inc. and may not be duplicated, copied, altered or removed from company without prior approval from Worldwide Quality Assurance or in compliance with Worldwide Standard Operating Procedures.		
REF: Worldwide-TMP-QA-001f-1.3	Page 44 of 49	

Worldwide Clinical Trials Controlled Quality Management Document		
WORLDWIDE CLINICAL TRIALS	Sponsor:	Integrative Research Laboratories Sweden AB
	Protocol Number:	IRL790C005
STATISTICAL ANALYSIS PLAN. PHASE 2-3-4		

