11.1.5. Vital Signs

Pulse and systolic/diastolic BP will be measured in supine position after five minutes of rest and then after 1 minute and 3 minutes in standing position, without sitting in between. Any symptomatic orthostatic reaction will be noted in the CRF (no/yes).

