14.10. Safety Analyses

Safety evaluations include AEs and concomitant medications reporting, complete physical examination, vital signs, 12-lead ECG (at rest), C-SSRS rating and clinical safety laboratory tests (clinical chemistry, haematology, urinalysis and coagulation). All will be presented as data summaries. No formal statistical analyses will be performed.

AEs and concomitant medications are recorded throughout the investigational period with the rest performed at screening, Visits 3, 4 and 5 and Visit 6 (follow-up) 5-8 days after last administration of IMP).

All safety and tolerability evaluations will be presented by the treatment received for the SS population.

All safety evaluations will be presented as interval or categorical data summaries (as appropriate) according to treatment group and day of assessment (if appropriate) for the safety population. No formal statistical analyses will be performed.

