6.2.9 Vital Signs

For blood pressure and pulse rate, the orthostatic changes will be calculated as standing minus supine readings. Patients meeting the following criteria will be identified:

- Patients with > 20 mmHg reduction (standing minus supine) in systolic blood pressure at 1 minute or 3 minutes of standing.
- Patients with > 10 mmHg reduction (standing minus supine) in diastolic blood pressure at 1 minute or 3 minutes of standing.

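### SAP 6.17.3 uses seated or prone readings as the supine reference for orthostatic change, contrary to the plan's own definition; with a seated reference, postural falls are likely to be undercounted.

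*SAP*

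**What the plan says.** Protocol 11.1.5 fixes the procedure: pulse and blood pressure are "measured in supine position after five minutes of rest and then after 1 minute and 3 minutes in standing position, without sitting in between". The CRF also holds a no/yes item for symptomatic orthostatic reactions.

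SAP 6.2.9 carries this into the derivation: "the orthostatic changes will be calculated as standing minus supine readings". Its two criteria repeat the reference posture:

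- Systolic: "Patients with > 20 mmHg reduction (standing minus supine) in systolic blood pressure at 1 minute or 3 minutes of standing".
- Diastolic: "Patients with > 10 mmHg reduction (standing minus supine) in diastolic blood pressure at 1 minute or 3 minutes of standing".

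SAP 6.17.3 plans summaries of supine values, standing values and the orthostatic change. It then adds: "Measurements taken either seated or prone will be considered taken supine". The next sentence plans the tabulation of patients meeting the criteria: "The number and percentage of patients with either >20 mmHg reduction in systolic blood pressure after standing", or the diastolic criterion, or both. All vital sign data are to be listed.

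No reason is given for the posture rule. It is not in Protocol 14.10.5 (Vital signs) and is not among the changes in SAP section 9. No summary without the affected readings is planned.

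**The concern.** The criteria are defined against a supine reference, but the rule lets a reading in another posture stand in for it. Standing minus seated is a different quantity from standing minus supine. In a patient whose pressure falls on becoming upright, some of the fall has already happened by the time of a seated reading, so the recorded change is smaller than the defined one. Those are the patients the criteria are meant to find.

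The outcome is relevant to this drug. Postural dizziness, dizziness, balance disorder and fall are among the potential adverse events in Protocol Table 4, and clinically significant symptomatic orthostatic hypotension is an exclusion criterion. Safety is judged from descriptive tables only. A table labelled as standing minus supine that silently mixes reference postures does not show what its label says.

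The same relabelling enters the supine summaries. If a patient is seated at one visit and supine at another, the change from baseline in the supine value includes a difference due to posture.

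**Working it through.** The plan gives no figure on this point, so there is none to reproduce. The check is a comparison of the texts, then algebra, then an illustration on assumed values.

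**Comparison of texts**

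| Place | Reference for orthostatic change |
|---|---|
| Protocol 11.1.5 | Supine after five minutes' rest, then standing, no sitting in between |
| SAP 6.2.9 | Supine, in the general definition and in both criteria |
| SAP 6.17.3 | Supine, but seated or prone readings count as supine |

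A seated or prone reference is therefore a departure from the protocol procedure. The SAP accepts it into the derivation with no mark in the summary table.

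**Algebra**

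Let D be the true fall (supine minus standing), s the supine minus seated pressure, and T the threshold (20 systolic, 10 diastolic).

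- Recorded fall with a seated reference = seated − standing = (supine − standing) − (supine − seated) = D − s.
- The patient is counted if D − s > T, that is, if D > T + s.
- If s > 0, patients with T < D ≤ T + s are missed. Anyone who is counted has D > T + s > T and is a true case.
- If s = 0, nothing changes.
- If s < 0, patients with T + s < D ≤ T are counted wrongly, and the count rises.

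Example, assuming s = 5 to 10 mmHg systolic: a true fall of 25 mmHg is recorded as 25 − 10 = 15 up to 25 − 5 = 20 mmHg, and neither exceeds 20. On the same assumption the missed band is above 20 and up to 25 (s = 5) or 30 mmHg (s = 10). Larger falls are still counted.

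**Illustration**

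Every input here is an assumption; none comes from the documents. Take true falls as normal, with mean 8 and SD 13 mmHg systolic, and mean 2 and SD 8 mmHg diastolic. Let f be the share of references that were seated.

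- True share above threshold: p0 = 1 − Φ((T − mean)/SD). Systolic: 1 − Φ(12/13) = 17.8%. Diastolic: 1 − Φ(8/8) = 15.9%.
- Share if every reference is seated: p1 = 1 − Φ((T − mean + s)/SD). For example, systolic with s = 5: 1 − Φ(17/13) = 9.5%.
- Share reported: (1 − f) × p0 + f × p1.

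| Criterion | s (mmHg) | f = 2% | f = 10% | f = 100% |
|---|---|---|---|---|
| Systolic >20 (true 17.8%) | 2 | 17.7% | 17.4% | 14.1% |
| | 5 | 17.6% | 17.0% | 9.5% |
| | 8 | 17.6% | 16.6% | 6.2% |
| | −3 | 17.9% | 18.5% | 24.4% |
| Diastolic >10 (true 15.9%) | 2 | 15.8% | 15.3% | 10.6% |
| | 5 | 15.7% | 14.8% | 5.2% |
| | 8 | 15.6% | 14.5% | 2.3% |
| | −3 | 16.1% | 16.9% | 26.6% |

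Direction follows the sign of s. Size follows s and f together, and at low f the shift is a few tenths of a percentage point or less.

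**The case against.** A reader might infer that the rule makes every orthostatic count too low, for seated and prone references alike and for both criteria. The documents do not support that.

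- **Prone.** Prone is a lying posture, so the argument about part of the fall having already occurred does not apply. The substitution is unexplained, but no downward bias has been shown.
- **Sign of s.** The documents give no supine–seated difference. It could be near zero or negative, and it may differ between systolic and diastolic pressure. A negative s raises the count.
- **Number of readings.** The protocol asks for supine and standing pressure wherever vital signs are taken, so the rule reaches only departures from procedure. There may be few or none.
- **Other sources.** The orthostatic count is not the only view of postural effects. Adverse events are tabulated by system organ class and preferred term, and the CRF holds the symptomatic-reaction item. The rule is openly stated, and listings show data as recorded on the eCRF.
- **Consequence.** Protocol 14.10 says of safety data: "No formal statistical analyses will be performed". The rule is the same in every arm.
- **Remedy.** Simply setting seated-reference changes to missing could worsen an undercount. When s > 0, a recorded fall above the threshold is certainly a true one. Discarding it while keeping all patients in the denominator can only lower the count or leave it unchanged.

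All of this stands, and it limits the direction, the size and the remedy. It does not remove the conflict between SAP 6.17.3 and the definition in SAP 6.2.9. Neither the adverse event tables nor the listings correct a summary table whose label does not match its contents.

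**Conclusion.** The point holds in a limited form. SAP 6.17.3 departs from the standing-minus-supine definition in SAP 6.2.9 and from the procedure in Protocol 11.1.5. For seated references, undercounting against the 20 and 10 mmHg criteria is the likely direction, on the assumption that pressure falls on becoming upright (s > 0). For prone references the direction is unclear.

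The size cannot be established, because the documents give neither s nor the number of readings affected. The illustrative figures show how the effect scales and do not estimate it for this trial. This is a minor point about descriptive safety tables, but the tabulated quantity should match its definition.

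**What to change.** Replace the posture sentence in SAP 6.17.3 with a rule to this effect:

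1. Derive orthostatic change, and the counts and percentages above 20 and 10 mmHg, only from true supine–standing pairs.
2. Limit the denominator to patients with at least one such pair, so that excluded readings do not lower the percentage by construction.
3. Report the number of seated and prone references by arm and visit.
4. Show the recorded position in the listing.
5. Keep the present all-readings rule as a sensitivity summary, so that falls already above the threshold from a seated reference are not lost.

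The cost is a short SAP edit, one extra summary, and a few missing orthostatic values in the main table. If position was not captured in the CRF, items 1 to 4 cannot be carried out for those readings, and the report should say so. Efficacy, alpha and power are not affected.
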